Evaluation (Cohort 4, Steps 3 and 4; standard)	Week 4 / Day 28 (+/- 48hr)	Week 5 / Day 29 (24 hr post-infusion)	Week 5 / Day 31 (72 hr post-infusion)	Week 5 / Day 35 (7 days post- infusion)	Weeks 6 to 13 (conditional ¹	Week 6 / Day 42 (+/- 48hr)	Week 7 / Day 43 (24 hr post-infusion)	Week 7 / Day 45 (72 hr post-infusion)	Week 7 / Day 49 (7 days post- infusion)	Week 8 / Day 56	Week 11 (±3 days)	Week 16 (± 7 days)	Week 24 (± 7 days)	Prem. Tx and/or S
Assessment														
PK RMD (Collection times are from the start of the infusion)	X Hr 0 & Hr 4					X Hr 0 & Hr 4								
PK ARVs (Collection time is from the start of the infusion)	X Hr 0	х				X Hr 0	х							
¹ These "conditional" er 6.2.3). If infusion will b			•	•	•			elayed for	the next S	Step.	(See	secti	on	

61

			Step 2 Infusior					Step Infusio			/ D/C
Evaluation (Cohort 4, Steps 2 and 3; delayed infusion)	Reg. to Step 2 ¹	R + 1 day (24 hr post-infusion)	R + 3 days (72 hr post-infusion)	Week R + 1 (7 days post- infusion)	Weeks R+2 to R+ 9 (conditional) (See section 6.2.3)	Reg. to Step 3 ¹	R + 1 day (24 hr post-infusion)	R + 3 days (72 hr post-infusion)	Week R + 1 (7 days post- infusion)	Weeks R+2 to R+ 9 (conditional) (See section 6.2.3)	Prem. Tx and/or Study
Clinical Assessments	х	Х	х	х	Once each week	х	х	х	х	Once each week	х
Targeted Physical Exam	Х	х	х	х	Once each week	х	Х	х	х	Once each week	x
Hematology	x	х	х		R+4 & R+8 (Weekly)	х	х	х		R+4 & R+8 (Weekly)	x
Potassium and Magnesium (see section 6.3.7 for timing at Pre-entry)				х	R+ 4 & R+ 8 (Weekly)				x	R+4 & R+8 (Weekly)	
LFTs/Blood Chemistries (see section 6.3.7)				х	R+2 & R+6				х	R+2 & R+6	х
Urine Pregnancy Testing	Х					Х					
ECG	X Hr 4		As clinica	lly indicat	ed	X Hr 4		As clinio	cally indic	ated	
CD4%	Х	Х	Х			Х	Х	Х			Х
¹ Registration to step week (R	l) is def	ined as or	ne week p	ast the w	eek of the la	ist visit on	the pre	vious ste	ep.		

6.1.4 Table 6.1.4-1: Cohort 4 Delayed Infusion SOE, Steps 2 and 3

			Step 2 Infusior					Step Infusio			y D/C
Evaluation (Cohort 4, Steps 2 and 3; delayed infusion)	Reg. to Step 2 ¹	R + 1 day (24 hr post-infusion)	R + 3 days (72 hr post-infusion)	Week R + 1 (7 days post- infusion)	Weeks R+2 to R+ 9 (conditional) (See section 6.2.3)	Reg. to Step 3 ¹	R + 1 day (24 hr post-infusion)	R + 3 days (72 hr post-infusion)	Week R + 1 (7 days post- infusion)	Weeks R+2 to R+ 9 (conditional) (See section 6.2.3)	Prem. Tx and/or Study

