6.2.3 Post-Entry Evaluations

The RMD/placebo infusion should be completed in 4 hours. In the event that the infusion requires more than 4 hours, the time of infusion completion is still to be considered Hour 4.

Post-Treatment Evaluations, Cohorts 1 – 3

Hour 4 evaluations begin immediately following completion of RMD/placebo infusion. All subsequent evaluation time points are to be calculated from the infusion completion time which is considered Hour 4 regardless of whether the actual time from infusion start to completion took less or more time than 4 hours (ie, Hour 6 is 2 hours after the infusion has finished, Hour 8 is 4 hours after the infusion has finished, etc.).

Post-Treatment Visit Schedule, Cohorts 1 – 3

Study visits and collection time points must be scheduled as indicated in the Schedule of Events (SOE) \pm 15 minutes for Hour 2, 4 (except for ECG which has a window of +0-60 minutes), 6, 8, 12; \pm 2 hours for Hour 24; \pm 4 hours for Hour

48/Day 2; \pm 2 days for Day 7 and Week 2/Day 14, and -1 day to +2 days for Week 4/Day 28. Per sections 6.2.4 and 7.1, participants may be required to return for a Week 8/Day 56 visit \pm 4 days.

Study Completion Evaluations, Cohorts 1 – 3

Week 4/Day 28 evaluations will serve as the study completion evaluations for participants who have maintained an HIV-1 RNA level of < 200 copies/mL by standard ultrasensitive assay since the Day 7 visit. See section 6.2.4 for participants who have an HIV-1 RNA level of \geq 200 copies/mL at the Day 7 visit.

Also, these evaluations will be the study completion evaluations for participants who did not experience any \geq Grade 3 AE or clinical event (per section 7.1).

Post-Entry Visit Schedule, Cohort 4

Study visits and collection time points must be scheduled as indicated in the Cohort 4 SOE, section 6.1.3. The windows are ±6 hours for day 1 (24 hours post-infusion), ±1 day for day 3 (72 hours post-infusion), and ±1 day for day 7 (7 days post infusion). For participants whose second, third, and/or fourth infusion must be delayed for any reason, the Delayed Infusion SOE, section 6.1.4, must be followed until the end of the study follow-up for that participant. Participants' visits will be scheduled per this SOE beginning with the first delayed infusion.

Sites should notify the A5315 core team if any infusion will be delayed ([contact]).

Conditional Evaluation Weeks, Cohort 4

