Record and key within 2 business days, the RMD/placebo infusion, including dose administered, whether administration was temporarily halted for any reason, duration of infusion, and whether the full dose was administered. If the infusion is temporarily halted, the schedule of evaluations should resume following completion of the RMD/placebo infusion (referred to as Hour 4, regardless of whether the actual time from infusion start to completion took more time than 4 hours). See sections 6.2.3 and 6.3.11. Record any unscheduled discontinuation of RMD or placebo for RMD.

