10.2 Pharmacology Study Design

This is a dose-finding trial of RMD at dose levels of 0.5, 2.0, and 5.0 mg/m². Participants in Cohorts 1 – 3 will be receiving an EFV-, DTG-, or RAL-based regimen that includes two N(t)RTIs. In Cohort 4, participants will be receiving a DTG- or RAL-based regimen that includes twp N(t)RTIs. PIs are not permitted in any cohort nor are other ARVs that are eliminated by or induce CYP3A4 (e.g., maraviroc, etravirine, rilpivirine).

Cohorts 1 – 3

The last ARV dosing taken prior to infusion will be recorded as a part of the entry/Hour 0 evaluation. A baseline whole blood sample (4 mL) will be drawn at pre-infusion entry/Hour 0 (within 15 minutes prior to RMD administration). RMD/placebo will be administered intravenously over a 4 hour infusion. Post infusion whole blood samples will be collected following completion of the RMD-infusion from the opposite side of the body, at 4, 6, 12, and 24 hours after initiation of RMD dosing. RAL, EFV, or DTG plasma levels will also be quantitated from these samples.

Cohort 4

The last ARV dosing taken prior to infusion will be recorded as a part of the Hour 0 evaluation for Steps 3 and 4. In each of these two steps, a whole blood sample will be drawn at pre-infusion /Hour 0 (within 15 minutes prior to RMD/placebo administration). RMD/placebo will be administered intravenously over a 4-hour infusion. Post-infusion whole blood samples will be collected from the opposite side of the body, at 4 and 24 hours after initiation of the infusion. **RMD plasma levels will be quantified from the 4-hours post-infusion sample and** DTG or RAL plasma levels will be quantitated from the **24-hours post-infusion** sample.

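### The romidepsin PK sampling clock runs from infusion start in some sections and from infusion completion in others, so the single Cohort 4 post-dose sample has no settled time when an infusion departs from 4 hours

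*Protocol*

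**What the plan says.** **Start clock.** In protocol Tables 6.1.3-2, 6.1.4-1 and 6.1.4-2 the Cohort 4 romidepsin row, sampled at Hr 0 and Hr 4, is headed "PK RMD (Collection times are from the start of the infusion". The SAP's Appendix 1 repeats the note. Section 10.2 places the Cohorts 1-3 draws "at 4, 6, 12, and 24 hours after initiation of RMD dosing" and the Cohort 4 draws "at 4 and 24 hours after initiation of the infusion".

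**Completion clock.** Section 6.2.3, ahead of any cohort heading, says "In the event that the infusion requires more than 4 hours, the time of infusion completion is still to be considered Hour 4". For Cohorts 1-3 it adds "All subsequent evaluation time points are to be calculated from the infusion completion time which is considered Hour 4", whether the infusion ran short or long. Section 6.3.4, with no cohort limit, treats completion of a temporarily halted infusion the same way: "referred to as Hour 4, regardless of whether the actual time from infusion start to completion took more time than 4 hours".

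**Mixed wording.** The 10.2 sentence that gives the Cohorts 1-3 times also says "Post infusion whole blood samples will be collected following completion of the RMD-infusion". For Cohort 4, 10.2 states "RMD plasma levels will be quantified from the 4-hours post-infusion sample", and 6.3.11 speaks of Hour 4 after the third and fourth infusions.

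**Windows and analysis.** Section 6.2.3 allows 15 minutes either side of Hour 4 in Cohorts 1-3. Its Cohort 4 windows begin at the 24-hour visit, so Hr 4 has none. Section 10.3 takes Cmax from the observed data and AUC by the linear-up/log-down trapezoid. It does not say whether actual or nominal times are used. SAP 7.11.6 and 7.14.5 plan only a table of pharmacologist-estimated parameters.

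**The concern.** The protocol foresees infusions that overrun or are halted. In exactly those cases a site cannot satisfy all the passages. Drawing at 4 hours from the start, as the Cohort 4 tables say, means drawing before the infusion ends. Drawing at completion, as 6.2.3 and 6.3.4 imply, departs from the table note. In Cohorts 1-3, one sentence of 10.2 requires both 4 hours from initiation and after completion, which is impossible if the infusion overruns.

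Evaluating romidepsin pharmacokinetics is the primary objective of the pharmacology plan (10.1), and PK parameters are a secondary outcome (9.2.2.5). Cohort 4 has one post-dose romidepsin sample per sampled infusion (the third and fourth), so no neighbouring sample would reveal a mistimed draw. The observed Cmax is whatever that sample shows.

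**Working it through.** No figure in the plan attaches to this point, so there is nothing to reproduce first.

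**Inputs from the protocol.** Planned infusion of 4 hours (6.2.3). Terminal half-life of about 3 hours (2.2, at 14 mg/m² in lymphoma patients). AUC rule (10.3).

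**Assumptions.** One compartment, constant-rate infusion, half-lives of 2 to 4 hours as a range, and infusion lengths other than 4 hours.

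**Rate constant.** k = ln 2 / 3 = 0.231 per hour. Then exp(-k) = 0.794, exp(-2k) = 0.630, exp(-3k) = 0.500, exp(-4k) = 0.397 and exp(-5k) = 0.315.

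**1. Exact 4-hour infusion.** Start and completion clocks name the same moments, so the ratio is 1.00 at Hours 4, 6 and 12.

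**2. Infusion lasting 5 hours at a steady rate.**
- Concentration at 4 h from the start relative to the end: (1 - 0.397) / (1 - 0.315) = 0.603 / 0.685 = 0.88, about 12% low.
- Half-life 2 h: (1 - 0.250) / (1 - 0.177) = 0.91. Half-life 4 h: (1 - 0.500) / (1 - 0.420) = 0.86. The range is about 9% to 14% low.

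**3. Infusion halted for 1 hour and finished at 5 h.** C(4)/C(5), in units of infusion rate over k:
- Halt 1-2 h: (0.206 × 0.500 + 0.370) / (0.206 × 0.397 + 0.500) = 0.473 / 0.582 = 0.81.
- Halt 2-3 h: (0.370 × 0.630 + 0.206) / (0.370 × 0.500 + 0.370) = 0.439 / 0.555 = 0.79.
- Halt 3.5-4.5 h: (0.555 × 0.891) / (0.555 × 0.707 + 0.109) = 0.494 / 0.501 = 0.99.

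These cases span about 1% to 21% low. They are illustrations, not bounds. A halt at 3-4 h gives (0.500 × 0.794) / (0.500 × 0.630 + 0.206) = 0.397 / 0.521 = 0.76. A halt just before Hour 4 can reverse the sign: for 3.75-4.75 h, (0.580 × 0.944) / (0.580 × 0.749 + 0.056) = 0.547 / 0.490 = 1.12.

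**4. Post-infusion label read literally.** A draw 4 h after the end of infusion would be at exp(-4k) = 0.397 of the end-of-infusion level, about 60% low. With a 4-hour half-life it is 0.50, and with 2 hours 0.25, so 50% to 75% low.

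**5. Actual versus nominal times, Cohorts 1-3, 5-hour infusion.** With dose and volume set to 1, true AUC is 1/k = 4.328. Completion-based samples fall at 5, 7, 13 and 25 h, with 0.593 at the first and 0.006 at the last.
- The declining part is (0.593 - 0.006) / 0.231 = 2.54 on either labelling, since the intervals are 2, 6 and 12 h both ways.
- The rising part is 0.5 × 5 × 0.593 = 1.48 with actual times, and 0.5 × 4 × 0.593 = 1.19 with nominal times.
- AUC0-24 as a share of the truth is (1.48 + 2.54) / 4.328 = 0.93 with actual times, and (1.19 + 2.54) / 4.328 = 0.86 with nominal times.

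**The case against.** The strongest reply is that the overrun rule already exists. The general sentence in 6.2.3 and the halted-infusion text in 6.3.4 apply to all cohorts, so a careful site would draw at completion. That is a reasonable reading, and it is why the fix adopts it. It still leaves the note in three tables and the Cohort 4 sentence of 10.2 saying something else.

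Three stronger readings are tempting, and the documents do not support them:

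- **That Cohort 4 samples will be drawn 4 hours after the infusion ends.** The 10.2 sentence just before the label places the draw 4 hours after initiation, and the tables agree. The 60% figure measures a labelling risk, not an instructed draw.
- **That the decline curve in Cohorts 1-3 is displaced as a whole.** The clocks coincide for the planned infusion and differ only by actual duration minus 4 hours. The documents give no frequency of overruns.
- **That Cmax and AUC cannot be compared.** Section 6.3.4 records infusion duration and halts. With actual times, the modelled AUC for a 5-hour infusion is 0.93 of the truth on either clock. Cohort 4, with only Hr 0 and Hr 4, supports no usable AUC on any clock. No Cohort 3 versus Cohort 4 PK comparison is planned: 10.3 compares parameters across background antiretrovirals.

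Also fair: between-person spread is large. Two of the Cmax entries in Table 2.2-2 give SD/mean of 22.2/35.6 = 0.62 and 31.7/49.5 = 0.64. The manual of procedures and lab processing chart, not available here, may settle some timing details. They would not remove a contradiction within the protocol.

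**Conclusion.** The point holds as a contradictory sampling rule of limited reach. It bites only when the infusion departs from 4 hours, and the exposed quantity is observed Cmax from the only post-dose romidepsin sample per sampled Cohort 4 infusion.

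The size is about 12% for an assumed 5-hour infusion, and about 1% to 21% low in the three halts first worked. A halt ending at Hour 4 gives somewhat more, and a very late one can reverse the direction. In Cohorts 1-3 the remaining issue is which times enter the AUC, worth about 7 points (0.93 versus 0.86) for a 5-hour infusion.

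All of this rests on a one-compartment model, a half-life taken from lymphoma patients at a higher dose, and assumed infusion lengths. It should be corrected, but it does not undermine the PK plan as a whole.

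**What to change.** Reconcile the passages to one clock, with Hour 4 as the actual end of infusion, which 6.2.3 and 6.3.4 already provide.

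- **Cohort 4 timing.** Change the note in the romidepsin PK rows of Tables 6.1.3-2, 6.1.4-1 and 6.1.4-2 (and its copy in SAP Appendix 1), the Hour 4 wording in 6.3.11, and the Cohort 4 paragraph of 10.2.
- **Label and window.** Call the assayed sample the end-of-infusion (Hour 4) sample and give it a window. Cohorts 1-3 already have 15 minutes either side. At a 3-hour half-life, a 15-minute error moves the value about 4% to 6%.
- **Records.** Capture actual infusion start, stop and draw times. Duration and halts are already recorded under 6.3.4.
- **Cohorts 1-3.** Section 5.1 describes Cohorts 1-3 as already dosed, so those draws cannot be changed. State in 10.3 that PK parameters use actual elapsed times, and resolve the two conditions in the Cohorts 1-3 sentence of 10.2 to show which clock was followed.

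The cost is wording in a few places plus recorded clock times. There are no extra blood draws and no change to treatment.

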on days 1, 8, and 15 of a 28-day cycle, usually for multiple cycles. Following a 4-hour intravenous administration of RMD at 14 mg/m² on days 1, 8, and 15 of a 28-day cycle in patients with T-cell lymphomas, the terminal half-life (t1/2) was approximately 3 hours. No accumulation of RMD was observed after repeated dosing. Early clinical trials of RMD in CTCL patients revealed a potentially increased risk of QTc prolongation. As a result, the package insert for this drug indicates that it should not be given to a patient with a prolonged QTc. Side effects of RMD at the MTD include nausea, fatigue, vomiting, and anorexia. Common first cycle toxicities reported include bone marrow suppression and transient elevations of liver function tests [24-25, 32]. In clinical trials of RMD for T-cell lymphoma, bone marrow suppression has been associated with fatal and serious infections as well as reactivation of EBV and hepatitis B virus, RMD is predominantly metabolized by the cytochrome P450 enzyme CYP3A4. RMD is highly protein bound in plasma (92% to 94%) over the concentration range of 50 ng/mL to 1000 ng/mL with α 1-acid-glycoprotein (AAG) being the principal binding protein. Although there are no formal drug interaction studies for RMD, strong CYP3A4 inhibitors may increase plasma concentrations of RMD. RMD is also a substrate of the efflux transporter P-gp (ABSB1); hence drugs that inhibit P-gp may increase plasma concentrations of RMD. Finally, RMD competes with beta estradiol for binding to estrogen receptors, which inhibits their function (RMD Investigators Brochure v 10.0 May 2012).

HIV-infected	Fold increase	p value			
donor	over no drug control	vs. control			
1	4.8	0.03			
2	5.6	0.006			
3	14.0	0.0008			
4	3.0	0.0005			
5	5.9	0.02			
6	14.0	0.02			
7	5.2	0.00002			
8	2.8	0.01			
9	16.0	0.00003			
10	20.1	0.0003			
11	1.8	0.4			
12	5.8	0.005			
13	12.3	0.001			
	Avg = 8.6				
HIV-1 RNA levels were measured by Roche Taqman v2.0 at day 6 in culture supernatants of CD4+ memory T-cells from patients on suppressive ART. Intracellular HIV RNA was not measured.					

Table **2.2-1**: Induction of HIV-1 RNA *ex vivo*

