PBMCs (see section 6.3.10)		х	х	Х	х	Х			х	х	х			x

	ning	ntry	ntry								Ste	ep 2		
	Screening	Pre-Entry	Pre-Entry			Step 1			Step 2 Reg.					Study D/C
Evaluation (Cohort 4, Screening through Step 2; standard)	Day -60 to Day -36	Day -35 to Day -28	Day -14 to Day -3	Entry/ Hour 0 Pre- Infusion/Infusion	Week 1 / Day 1 (24 hr post-infusion)	Week 1/ Day 3 (72 hr post-infusion)	Week 1 / Day 7 (7 days post- infusion)	Weeks 2 to 9 (conditional) ¹	Week 2 / Day 14 (+/- 48hr)	Week 3 / Day 15 (24 hr post-infusion)	Week 3 / Day 17 (72 hr post-infusion)	Week 3 / Day 21 (7 days post- infusion)	Weeks 4 to 11 (conditional) ¹	Prem. Tx and St
Stored PBMC for virology testing (see section 6.3.10)		х	x	х	х	х			х	x	х			x
Histone Acetylation				Hr 0	х	х			Hr 0	х	х			
Stored PBMC for qVOA (see section 6.3.10)		х												
RMD/Placebo Infusion				Х					Х					
ART Adherence Assessment	х		х	х					Х					x
¹ These "conditional" evalua infusion will be delayed, go					-			will be delay	ed for th	ie next	Step.	(See se	ection 6.2.3).	lf

			Step 3	3				SI	tep 4					U
	Step 3 Reg.					Step 4 Reg.					st-Infi Follov		4	Study D/C
Evaluation (Cohort 4, Steps 3 and 4; standard)	Week 4 / Day 28 (+/- 48hr)	Week 5 / Day 29 (24 hr post-infusion)	Week 5 / Day 31 (72 hr post-infusion)	Week 5 / Day 35 (7 days post- infusion)	Weeks 6 to 13 (conditional ¹	Week 6 / Day 42 (+/- 48hr)	Week 7 / Day 43 (24 hr post-infusion)	Week 7 / Day 45 (72 hr post-infusion)	Week 7 / Day 49 (7 days post- infusion)	Week 8 / Day 56	Week 11 (±3 days)	Week 16 (± 7 days)	Week 24 (± 7 days)	Prem. Tx and/or S
Clinical Assessments	х	х	х	х	Once each week	х	х	х	х	х	Х	Х	Х	х
Targeted Physical Exam	Х	Х	Х	х	Х	х	х	х	Х	х	х	х	х	x
Hematology		х	х	х	Wk 8, 12 (Weekly – see 6.2.3)		х	х		х	x	x	х	x
Potassium and Magnesium (see section 6.3.7 for timing at Pre-entry)				х	Wk 8, 12 (Weekly – see 6.2.3)				x					
LFTs/Blood Chemistries (see section 6.3.7)				х	Wk 8, 12				х				х	x
Urine Pregnancy Testing	х					х					s clin indica		,	

Table 6.1.3-2: Cohort 4 Screening through Steps 3 and 4

			Step 3	3				St	tep 4					с
	Step 3 Reg.					Step 4 Reg.					st-Inf Follov		4	tudy D/C

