Stored Plasma and PBMC for immunology testing (see section 6.3.9)		х					x				x
Plasma HIV-1 RNA real time											x
Plasma HIV-1 RNA expedited				х	R+4 & R+8 (Weekly)				х	R+4 & R+8 (Weekly)	
Plasma HIV-1 RNA by SCA	х	Х	Х			х	х	Х			x
PBMCs (see section 6.3.10)	х	Х	Х			х	х	Х			x
Stored PBMC for virology testing (see section 6.3.10)	х	х	Х			Х	х	Х			x
Histone Acetylation	X Hr 0	Х	х			X Hr 0	х	х			
RMD / Placebo Infusion	Х					Х					

63

			Step 2 Infusior					Step Infusio			/ D/C
Evaluation (Cohort 4, Steps 2 and 3; delayed infusion)	Reg. to Step 2 ¹	R + 1 day (24 hr post-infusion)	R + 3 days (72 hr post-infusion)	Week R + 1 (7 days post- infusion)	Weeks R+2 to R+ 9 (conditional) (See section 6.2.3)	Reg. to Step 3 ⁻¹	R + 1 day (24 hr post-infusion)	R + 3 days (72 hr post-infusion)	Week R + 1 (7 days post- infusion)	Weeks R+2 to R+ 9 (conditional) (See section 6.2.3)	Prem. Tx and/or Study
ART Adherence Assessment	х					х					х
¹ Registration to step week (R	R) is def	ined as on	ne week p	ast the w	eek of the la	ast visit on	the pre	vious ste	ep.		
PK RMD (Collection times are from the start of the infusion)						X Hr 0 & Hr 4					
PK ARVs (Collection time is from the start of the infusion)						X Hr 0	x				
¹ Registration to step week (R	R) is def	ined as on	ne week p	ast the w	eek of the la	ast visit on	the pre	vious ste	ep.		•

64

				Step 4					>
Evaluation		Inf	usion 4		Pc	st-Infusic	on 4 Follow	/ Up	Tx or Study
(Cohort 4, Step 4; delayed infusion)	Reg. to Step 4 ¹	R + 1 day (24 hr post- infusion)	R + 3 days (72 hr post- infusion)	Week R + 1 (7 days post- infusion)	Week R + 2	Week R + 5	WeekR + 10	Week R + 18	Prem. Tx or D/C
Clinical Assessments	х	Х	Х	Х	Х	Х	Х	Х	Х
Targeted Physical Exam	Х	Х	Х	Х	Х	Х	Х	Х	х
Hematology	Х	Х	Х	Х	Х	Х	Х	Х	Х
LFTs/Blood Chemistries (see section 6.3.7)								х	х
Urine Pregnancy Testing	Х				A	s clinica	lly indicat	ed	
ECG	X Hr 4	As	clinically indic	ated	Х				
CD4%	Х	Х	Х		Х	Х	Х	Х	Х
Stored Plasma and PBMC for immunology testing (see section 6.3.9)		x			х	x	х	х	х
Plasma HIV-1 RNA real time					Х	х	х		Х
Plasma HIV-1 RNA expedited				х					

 Table 6.1.4-2:
 Cohort 4 Delayed Infusion SOE, Step 4

				Step 4					2
Evaluation		Inf	usion 4		Pc	st-Infusio	on 4 Follow	/ Up	· Stud

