Potassium and magnesium levels will be assessed 7 days prior to **the Steps 2**, **3**, **and 4** infusions. Blood potassium and magnesium values must be within normal limits. If the potassium and/or magnesium value is below the site's clinical laboratory's limit of normal, the participant should be supplemented as medically indicated, retested, and evaluated again within 3 days prior to the infusion. The repeated potassium and/or magnesium values must be within normal range for the site's limit of normal for the infusion to take place.

Given blood volume constraints in this study, sites should use pediatric volume tubes for checking potassium and magnesium levels whenever feasible.

Prior to the Steps 2, 3, and 4 infusions, if the potassium and magnesium levels are still out of range after retest, **c**onsultation with the core team is required before a decision about discontinuation is made ([contact]).

Blood Chemistries

All Cohorts

Electrolytes [sodium, potassium, chloride, phosphate, bicarbonate], calcium, magnesium, creatinine, blood urea nitrogen (BUN), and uric acid will be evaluated.

Calculated creatinine clearance estimated by the Cockcroft-Gault equation will be evaluated.

NOTE: A program for calculating creatinine clearance by the Cockcroft-Gault method is available on www.fstrf.org.

Urinalysis

Urinalysis with microscopic exam will be done at screening only.

Pregnancy Test

Pregnancy testing will be done per the SOE. For women of reproductive potential: Serum or urine β -HCG (urine test must have a sensitivity of \leq 25 mIU/mL).

For Cohort 4, only urine pregnancy testing is permitted.

Refer to section 7.2 for details on pregnancy and pregnancy outcome reporting.

Hepatitis Screen

HBsAg and HCV antibody testing will be done per the SOE. HCV RNA testing is required if HCV antibody positive. See sections 4.1.9, 4.1.10, 4.3.7, and 4.3.8 for details.

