7.1.5 Cardiac Toxicity

Refer to the A5315 MOPS for the DAIDS Toxicity Table to grade QTc prolongation.

- Grade 1: Infusion should continue without interruption, at the discretion of the site investigator.
- Grade 2: Infusion should continue without interruption, at the discretion of the site investigator. A repeat ECG should be performed at the 7 and 14 days following the infusion.
- Grade 3 and 4: The infusion should be interrupted. If the Grade 3 QTc prolongation is considered to be most likely due to concomitant illness or medication, standard management, including discontinuation of the likely causative agent, should be undertaken. A repeat ECG should be performed 7 and 14 days after the infusion.

Several treatment-emergent changes in ECGs (including T-wave and STsegment changes) have been reported in clinical studies of RMD. The clinical significance of these changes is unknown. In this study, electrolytes and ECGs are monitored at Pre-Entry and then again after each infusion. The use of strong CYP3A4 inhibitors that may increase RMD concentrations is prohibited during the study. ECG changes observed in participants may be multifactorial. Clinicians should evaluate participants with ECG changes for other possible contributing factors and address any that are identified. Sites should contact the core team ([contact]) to help determine whether additional infusions should be cancelled.

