9.2 Outcome Measures

NOTE: Due to insufficient numbers of resting CD4+ T-cells available from some Cohort 4 participants to perform all the planned assays (e.g., cell-associated HIV-1 RNA, total HIV-1 DNA, histone acetylation, PTEF-b activation), those assays will be performed using peripheral blood mononuclear cells (PBMCs). The team carefully reassessed the priorities for the use of these cells based on advances in the field since the prior protocol version. Accordingly, the relevant objectives and outcomes measures sections have been updated.

- 9.2.1 Primary Endpoints
 - 9.2.1.1 Safety

Occurrence of Grade \geq 3 AE including signs/symptoms, lab toxicities, and /or clinical events that is probably, possibly or definitely related to study treatment (as judged by the core team, blinded to treatment arm) any time from the time of study treatment administration until 28 days after the administration.

- 9.2.1.2 Efficacy
 - 9.2.1.2.1 Change in plasma HIV-1 RNA levels from baseline (average of pre-entry and entry values) as detected by single copy assay at 24 and 48 hours (average) after the single administration of RMD or placebo in Cohorts 1 3.
 - 9.2.1.2.2 Change in plasma HIV-1 RNA levels from baseline (average of pre-entry and entry values) as detected by single copy assay before and 24 hours after each administration of RMD or placebo in Cohort 4.
 - 9.2.1.2.3 Change in cell-associated HIV-1 RNA levels in resting CD4+ T-cells from baseline to 24 hours after the single administration of RMD or placebo in Cohorts 1 – 3.
 - 9.2.1.2.4 Change in cell-associated HIV-1 RNA levels in **PBMCs** before and **24 hours** after each administration of RMD or placebo in Cohort 4.
- 9.2.2 Secondary Outcome Measures
 - 9.2.2.1 Changes in plasma HIV-1 RNA levels as detected by single copy assay from baseline to after the single administration of RMD or placebo in Cohorts 1 3 and after each administration of RMD or placebo in Cohort 4.

- 9.2.2.2 Change in cell-associated HIV-1 RNA levels in resting CD4+ T-cells from baseline to 14 days after the administration of RMD or placebo in Cohorts 1-3, and in PBMCs after each administration of RMD or placebo in Cohort 4.
- 9.2.2.3 Changes in histone acetylation in CD4+ **and CD8+** T-cells from baseline to after the single administration of RMD or placebo in Cohorts 1-3 and after each administration of RMD or placebo in Cohort 4.

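### After a delayed fourth infusion in Cohort 4, no liver or chemistry test is scheduled until Week R+18, so the 28-day primary safety window has none

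*Protocol*

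**What the plan says.** Protocol 6.2.3 moves any Cohort 4 participant whose second, third or fourth infusion is delayed to a separate schedule: "the Delayed Infusion SOE, section 6.1.4, must be followed until the end of the study follow-up for that participant". That schedule has two tables.

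- Table 6.1.4-1, "Cohort 4 Delayed Infusion SOE, Steps 2 and 3", marks liver tests/chemistries and potassium/magnesium at Week R+1, 7 days after the infusion, in each step.
- Table 6.1.4-2, "Cohort 4 Delayed Infusion SOE, Step 4", marks liver tests/chemistries only at Week R+18 and at premature discontinuation. It shows no potassium/magnesium row.

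The standard table, "Cohort 4 Screening through Steps 3 and 4" (Table 6.1.3-2), marks both rows at Day 49, 7 days after infusion 4.

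Protocol 9.2.1.1 defines the primary safety endpoint to include related laboratory toxicities of Grade 3 or higher, arising "any time from the time of study treatment administration until 28 days after the administration". Protocol 7.1.5 states: "In this study, electrolytes and ECGs are monitored at Pre-Entry and then again after each infusion".

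**The concern.** Only the delayed fourth infusion lacks the 7-day chemistry draw; every other Cohort 4 infusion, delayed or not, has one. Cohort 4 is there to establish the safety of repeated dosing, and the gap follows the last dose.

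The missing tests matter for this drug. Protocol 2.2 reports: "Common first cycle toxicities reported include bone marrow suppression and transient elevations of liver function tests". A transient, symptom-free liver elevation is the kind of event that testing driven by symptoms tends to miss. SAP 6.3 keeps every exposed participant in the safety analysis, and SAP 7.9.3 reports the primary safety outcome as a list of events. Nothing there separates a participant who was tested and clear from one who was not tested. For delayed participants, an empty entry for liver or chemistry events after infusion 4 would mean only that no test was scheduled.

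Potassium or magnesium out of range is one of the reasons an infusion can be delayed (Protocol 4.5.3, 4.7.3 and 4.9.3). Someone delayed for an electrolyte problem would then have less electrolyte follow-up after the last dose than someone never delayed.

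**Working it through.** The plan gives no figure to reproduce. The check compares the schedules and converts visit weeks to days after infusion 4.

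**Reading the columns.** Table 6.1.4-2 has nine columns: registration, R+1 day, R+3 days, Weeks R+1, R+2, R+5, R+10 and R+18, and premature discontinuation. The two liver/chemistry marks fall in columns 8 and 9. Other rows confirm the alignment, taking infusion 4 at Week 6 of the standard schedule:

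- Hematology fills all nine columns.
- The viral outgrowth samples fall at R+5 and R+18, and 6 + 5 = 11 and 6 + 18 = 24 match Weeks 11 and 24 of the standard table.
- ART adherence falls at registration, R+10 and R+18, and 6 + 10 = 16 and 6 + 18 = 24 match Weeks 16 and 24.

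**Days after infusion 4.** Week R+1 is labelled as 7 days post-infusion, so Week R+n is day 7n: R+1 = 7, R+2 = 14, R+5 = 35, R+10 = 70, R+18 = 18 × 7 = 126. On the standard schedule, Day 49 − Day 42 = 7 days, and (24 − 6) × 7 = 126 days.

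**The schedules side by side, for participants who stay on study:**

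| Schedule | Liver tests/chemistries after the infusion | Potassium/magnesium row |
|---|---|---|
| Standard, infusion 4 (6.1.3-2) | Day 7, day 126 | Day 7 |
| Delayed, infusions 2 and 3 (6.1.4-1) | Day 7, plus conditional weeks | Day 7, plus conditional weeks |
| Delayed, infusion 4 (6.1.4-2) | Day 126 | No row |

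**Inside the 28-day window after a delayed infusion 4.** The scheduled visits are at days 1, 3, 7 and 14.

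- Hematology: 4 of 4 visits.
- Liver tests/chemistries: 0 of 4 visits. The standard schedule has one draw, at day 7.
- First scheduled chemistry draw: day 126, and 126 − 28 = 98 days after the window closes.
- Infusions followed by a 7-day chemistry draw: 3 of 4 on the delayed path, 4 of 4 on the standard path.

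**Whether other text fills the gap.** Protocol 6.3.7 ties potassium and magnesium testing to the days before the Step 2, 3 and 4 infusions. The conditional weekly tests in 6.2.3 serve eligibility for a next infusion. After infusion 4 there is none, so neither provision applies.

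**The case against.** The reading of the liver/chemistry row is not in dispute; the objections concern its weight.

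- **What is missing is one scheduled draw.** Clinical assessments, targeted examinations and hematology continue at days 1, 3, 7 and 14, with ECGs at Hour 4 and Week R+2, and an abnormal unscheduled test would still count. This stands: the loss is of systematic ascertainment.
- **Early stoppers have some cover.** Participants who stop treatment early have discontinuation evaluations, including chemistries, 4 weeks after the infusion (Protocol 6.2.5). This also stands, so the point is limited to those who stay on study.
- **The standard schedule is itself thin.** Its single draw at day 7 would miss an elevation arising later and resolving before Week 24. That is true. The correction brings the two schedules level; it does not make the whole window well covered.
- **The toxicity evidence comes from lymphoma patients at 14 mg/m².** Protocol 2.2 describes first-cycle events at that dose, a half-life of about 3 hours, no accumulation, and no study-related Grade 3 or 4 events in a six-participant HIV trial of three 5 mg/m² doses. This lowers the expected yield. It does not explain why infusion 4 alone goes untested.
- **The potassium/magnesium argument is weaker.** Those tests mainly clear the next infusion, and the sentence in 7.1.5 sets no interval. The missing row should be checked against the typeset table. The liver/chemistry row carries the point for liver tests and creatinine without it.

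Blood-volume limits do not account for the omission: the delayed Step 4 table adds hematology at registration and Week R+1, where the standard table has none at Days 42 and 49.

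**Conclusion.** The concern holds. A site following Table 6.1.4-2 exactly would run no scheduled liver or chemistry test in the 28 days after infusion 4, although the primary endpoint counts laboratory toxicities in that window and 7.1.5 says electrolytes are monitored after each infusion. The size is 0 draws against 1 per delayed participant.

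This assumes that the 28-day window runs from infusion 4 as from any other infusion, and that the participant is neither discontinued early nor tested outside the schedule. Cohort 4 plans 15 participants, 12 on romidepsin; the number delayed is not given. No direction of bias between arms is claimed. The gap is narrow, but it lies in a primary endpoint and is easily closed.

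**What to change.** Mark liver function tests/blood chemistries at Week R+1 in Table 6.1.4-2, to match Day 49 in Table 6.1.3-2 and Week R+1 in Table 6.1.4-1. No separate electrolyte row is needed, because the chemistry panel in Protocol 6.3.7 already covers both: "Electrolytes [sodium, potassium, chloride, phosphate, bicarbonate], calcium, magnesium, creatinine, blood urea nitrogen (BUN), and uric acid will be evaluated".

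The cost is one cell in the table, with whatever amendment and IRB review that requires, and a little more blood from delayed participants only. No visit is added: Week R+1 already draws hematology and expedited HIV-1 RNA. The added volume has to fit within the study's blood limits.

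For anyone who has already passed that visit, the listing in SAP 7.9.3 should state how many delayed participants had any chemistry result in the 28 days after infusion 4.
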